14.2 Vascular Core Lab

Both pre-randomisation and trial procedure coronary angiogram, coronary angioplasty images, intracoronary imaging and peripheral vascular imaging will be transferred to a vascular core laboratory. Each participant's pre-randomisation BCIS JS and PCI procedural success will be independently validated by the core laboratory. The core laboratory will calculate a number of other scores reflecting the anatomic complexity of coronary disease, the extent of effective revascularisation and the complexity of CTO lesions.

This data will be used to conduct a number of sub-analyses to identify predictors of benefit for the primary and secondary outcomes. The core laboratory will subsequently provide the relevant data to the Sponsor and CTU at the London School of Hygiene & Tropical Medicine for analysis against the data held in the eCRF.

15. Randomisation

Potential patients will be reviewed by the Principal Investigator before randomisation with all available tests/notes to confirm eligibility.

Once the eligibility of a patient is confirmed by the trial coordinators and written informed consent obtained, randomisation will be carried out via an online web-based system. Randomisation of the treatment assignment will be stratified by centre using randomly permuted blocks of varying size, with 1:1 allocation between the LV-unloading and non-LV unloading arms.

There is no time limit from randomisation to PCI. However, it is recommended that index PCI be carried out as close as possible to randomisation to minimise the incidence of events prior to the assigned treatment. Clinical events that occur after randomisation but before planned PCI will be attributed to the assigned treatment on an intention-to-treat basis.

16. Percutaneous Coronary Intervention

16.1 Pre-procedure workup

Cross-sectional imaging of the peripheral vasculature with computed tomography (CT) angiography is strongly recommended in all patients prior to enrolment. Where significant peripheral vascular disease or access issues are identified, cases should be discussed in a multidisciplinary meeting with vascular surgeons and/or interventional radiologists to develop a safe access and closure plan prior to randomisation.

16.2 LV Unloading

The choice of pLVAD device is at the discretion of the operator: any CE marked device intended for the purpose of LV unloading during high-risk PCI may be used. Device placement should be performed prior to the start of the PCI and used according to the manufacturer's instructions. Femoral arterial access is preferred, but alternative routes of access (e.g. axillary, transcaaval may be utilised where local expertise permits). Use of ultrasound and/or fluoroscopy to guide femoral arterial puncture is mandated; the micro puncture technique is strongly advised where expertise permits. Device position should be documented fluoroscopically and if required, by echocardiography during the procedure. The maximal amount of haemodynamic support should be provided throughout the procedure.

At the end of the PCI procedure device support should be weaned and an assessment made of suitability for removal. Where possible, the device should be removed on-table prior to transfer of the patient. Otherwise, weaning of the device in the recovery area is recommended. The method of vascular closure is at the discretion of the operator and vascular surgical/interventional radiology experts. If ongoing haemodynamic support is required, the patient should be transferred to a critical care environment for ongoing monitoring and management.

Elective mechanical circulatory support is not permitted in the no-unloading arm, but may be used for bail-out following complications of the procedure (see 16.4 below)

16.3 Adjunctive therapy and devices

PCI will be performed according to local protocols. Measurement of LV end-diastolic pressure should be performed in all patients prior to PCI; right heart catheterisation for periprocedural haemodynamic monitoring may be used at the clinicians discretion. Dual antiplatelet therapy should be given in all cases, with pre-loading, and the post-PCI duration based on the individuals bleeding risk and local/national guidelines. Radial access is preferred for the PCI procedure. Drug-eluting stents are recommended. Intracoronary imaging (OCT or IVUS) is mandated for left mainstem PCI and strongly recommended for all other PCI procedures: a final intracoronary imaging acquisition following final balloon inflations is strongly recommended to assess the adequacy of PCI

16.4 Bailout

In patients assigned to receive no LV unloading, bail-out use of mechanical circulatory support will be permitted only in specific circumstances;

- Cardiogenic shock (persistent hypotension systolic blood pressure (SBP) <90mmHg for > 15 minutes and signs of organ hypoperfusion without response to vasoactive drugs)
- Profound hypotension (SBP <60mmHg) for > 3 minutes
- Significant pulmonary oedema requiring high-flow oxygen therapy or refractory to initial medical management
- Incomplete resolution of mechanical complication of PCI with persistently reduced angiographic flow and/or symptoms or signs of ischaemia
- Cardiac arrest requiring CPR

In such situations, the permitted mechanical circulatory support strategies will be IABP and/or veno-arterial extracorporeal membrane oxygenation (VA-ECMO). These events will be captured as pre-specified secondary outcome events. Crossover to pLVAD is not permitted and will be considered a protocol violation.

16.5 Staged Procedures

Where a second stage is required, this must be specified at the end of the first procedure and the second stage should be completed within the subsequent 6 weeks. In patients assigned to LV-unloading, use of an unloading device in the second stage is at the operator's discretion. In the no LV-unloading arm, elective mechanical circulatory support is not permitted, unless the procedure is a re-attempt following a prior failed PCI due to haemodynamic instability, in which case an IABP may be utilised.

16.6 Completeness of Revascularisation

It is strongly recommended that PCI is considered and, if feasible, attempted on all significant coronary lesions in major proximal coronary vessels (or side branches $>2.5\text{mm}$ in diameter) subtending viable myocardium. Lesion significance is defined as $>70\%$ diameter stenosis on angiography or for lesions between 50 and 70% diameter stenosis, when accompanied by demonstrable reversible ischaemia on invasive or non-invasive testing. Planned target lesions will need to be identified by the operator and recorded by the trial coordinator before the procedure.

The coronary disease burden at baseline and the degree of final revascularisation will be characterised by the BCIS-1 JS and SYNTAX scores and revascularisation index (RI), where $RI = (JS_{\text{pre}} - JS_{\text{post}})/JS_{\text{pre}}$.

16.7 Protocol adherence

Every effort should be made to adhere to the assigned treatment strategy.

In cases where, following randomisation to no LV-unloading, it is decided PCI cannot safely be performed without LV unloading (either due a change in clinical status or a failed attempt), consideration should be given to revascularisation with CABG; otherwise the patient should not undergo revascularisation.

In cases where, following randomisation to LV-unloading, it is decided pLVAD insertion cannot safely be performed, PCI may be performed with an alternative MCS device or without device support.

17. Coronary physiology substudy

17.1 Aim

One of the proposed beneficial mechanisms of action for the pLVAD is to improve coronary flow and to potentially protect the coronary microvasculature during PCI. Post PCI physiology measurements have failed to show an improvement in flow with a pLVAD however, pre-PCI where autoregulation is likely to be disabled an improvement in flow may be seen but this is yet to be investigated. This substudy therefore aims to establish whether LV unloading with pLVAD leads to an improvement in coronary flow pre PCI and a greater improvement in coronary flow reserve from before to after PCI, than standard high-risk PCI without pLVAD. The results of the substudy will give a deeper mechanistic understanding of how a pLVAD impacts on myocardial oxygen supply and therefore could potentially help explain the findings of the main CHIP-BCIS3 study.

17.2 Site selection

Participation in the substudy is optional for trial sites participating in the main trial.

17.3 Consent

Patients approached to participate in the main trial at substudy sites will be invited to join the substudy. Participation in the substudy will be optional and patients may participate in the main trial without participating in the substudy.

17.4 Sample size

We aim to recruit a minimum of 44 patients to detect a difference in post-PCI CFR of 0.5 (at a significance level of 5% and power of 90%) between the elective unloading and standard care groups.

17.5 Methods

Measurements of coronary flow will be made pre- and post- PCI using a coronary pressure guidewire equipped with a temperature sensor (Abbot Pressurewire X), using standard clinical methods. In both groups transit time will be measured at rest and repeated with hyperaemia induced with intravenous adenosine.

In the elective unloading group transit time will also be measured with the pLVAD active at maximal setting both before and after PCI.

18. Medical Therapy

It is recommended that all patients receive guideline directed medical therapy following the procedure. Drug classes to be considered include:

- Aspirin
- P₂Y₁₂ inhibitor
- High-potency statin
- ACE inhibitor
- Beta-blocker
- Mineralocorticoid receptor antagonist
- Anticoagulation where appropriate

19. Data Collection and Follow-Up

19.1 Data handling

Data will be collected via an electronic Case Report Form (eCRF), managed by Sealed Envelope Ltd. and hosted by Rackspace. In accordance with GCP, the electronic data entry system will be validated and Working Practice Documents covering its use will be drafted and maintained.

The eCRF will be accessed by users through a normal web browser (e.g. Internet Explorer). Each user will have their own individual account and secure password. Only personnel authorised by the LSHTM CTU will be granted access to the eCRF. Centres will only be able to access data for participants recruited at their centre. Direct access to the eCRF will be granted to authorised representatives from the Sponsor, host institution and the regulatory authorities to permit trial-related monitoring, audits and inspections. eCRFs should be completed within 2 weeks of each trial milestone where possible.

Principal Investigators at each site have overall responsibility for the accuracy, completeness and legibility of the data entered onto the eCRF and associated reports.

Trial participants will be identified by a unique trial specific number and/or code in any database. The name and any other identifying detail will not be included in any trial data electronic file. Patient data will be kept confidential and managed in accordance with the Data Protection Act (2018), NHS Caldecott principles, the Research Governance Framework for Health and Social Care, and the CHIP-BCIS3 Protocol, Version 1.4, 22 May 2024
ISRCTN 17730734, IRAS 290599

conditions of Research Ethics Committee Approval. Personal patient data will be stored for a maximum of 8 years at the research sites.

Data will be pseudonymised and will not contain any identifiable data, apart from NHS number which will be encrypted and stored separately from the other data. This will be used to link patients to HES data through NHS England. NHS numbers will be stored for up to 10 years following enrolment.

19.2 NHS England

There will be two occurrences of data linkage with HES data through NHS England (formerly NHS Digital). A list of trial IDs, date of randomisation, NHS numbers and dates of birth will be prepared and securely sent to NHS England. In turn, NHS England will provide number of events of death, stroke, myocardial infarction and cardiovascular hospitalisation that occur between the date of randomisation and date the data linkage was run. These data will be used to validate the main trial dataset and identify with high sensitivity any endpoints missed by traditional follow up methods.

19.3 Tests required for eligibility

The following tests are required for identifying and screening patients. These are all standard of care tests and must be performed before patient consent:

- Demographics and medical history
- Coronary angiogram
- LVEF assessment

19.3.1 Time limits for screening tests

Eligibility criteria	Test	Time limit
Extensive coronary disease	Coronary angiogram	Clinically valid
Severe LV systolic dysfunction	Echocardiogram, cardiac MRI	1 year prior to randomisation

19.4 Trial Checklist

	Tests required for eligibility	Baseline	Pre-PCI	Peri-procedural	Post-procedure (6 hours)	Post-procedure (24 hours)	At discharge (up to 24 hours) post- PCI	At 90 days post- randomisation	At 1-year post- randomisation	Yearly Follow-up	End of trial follow- up
Clinical assessments (standard of care)											
Demographics and med. history	X										
Coronary angio	X										
LVEF assessment	X										
Viability assessment		X									
FBC	X						X				
Creatinine and electrolytes	X		X				X				
HbA1C		X									
Full lipid profile		X									
Troponin T/I		X	X		X	X					
Haemodynamics				X							
Procedural details including device insertion				X							
Vasoactive medication				X							
ECG		X					X				
Intravascular imaging				X							
Trial specific assessments											
LVEDP				X							
BNP/NT-proBNP		X									
NYHA/CCS		X						X	X	X	X
EQ-5D-5L		X						X	X	X	X
KCCQ		X						X	X	X	X
Primary Endpoint							X	X	X	X	X
Secondary Endpoints							X	X	X	X	X
SAEs							X	X	X	X	X
Cardiac Medication		X					X	X	X	X	X

Baseline (up to 6 months prior to randomisation):

- Coronary anatomy and planned PCI procedure
- Viability study (If available)
- Cross-sectional imaging of peripheral vasculature (If available)
- LVEF
- Full blood count
- Creatinine and electrolytes
- HbA1c
- ECG
- Troponin T or I
- BNP/NT-proBNP
- NYHA/CCS
- EuroQoL EQ-5D-5L
- KCCQ
- Cardiac Medication

Pre-PCI (within 24 hours of procedure):

- Troponin T or I
- Creatinine and electrolytes

Peri-procedural

- Haemodynamics
- Procedural details including device insertion
- Vasoactive medication
- Intravascular imaging

Post-procedure (6 hours after end of procedure)

- Troponin T or I

Post-procedure (24 hours after end of procedure if patient remains in hospital)

- Troponin T or I
- ECG

At discharge – if PCI is staged please collect for each stage of the procedure:

- Death
- Stroke
- MI
- Cardiovascular Hospitalisation
- Creatinine and electrolytes
- Cardiac medication
- SAE

90 days after randomisation (telephone follow-up, or in person if the participant is due to attend hospital for a clinical visit):

- Death
- Stroke
- MI
- Cardiovascular Hospitalisation
- Major bleeding
- Unplanned further revascularisation
- NYHA/CCS
- EuroQoL EQ-5D-5L
- KCCQ
- Cardiac medication
- Acute Kidney Injury
- SAE

Yearly after randomisation (telephone follow-up, or in person if the participant is due to attend hospital for a clinical visit):

- Death
- Stroke
- MI
- Cardiovascular Hospitalisation
- Major bleeding
- Unplanned further revascularisation
- NYHA/CCS
- EuroQoL EQ-5D-5L
- KCCQ
- Cardiac medication
- SAE

End of trial follow-up (telephone follow-up, or in person if the participant is due to attend hospital for a clinical visit):

- Death
- Stroke
- MI
- Cardiovascular Hospitalisation
- Major bleeding
- Unplanned further revascularisation
- NYHA/CCS
- EuroQoL EQ-5D-5L
- KCCQ
- Cardiac medication
- SAE

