7.2 Major Secondary Endpoints

Combined primary endpoint analysed with a time-to-first-event method

Individual components of the primary endpoint (as well as repeated occurrences of these events)

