7.3 Other Secondary Endpoints

Major bleeding
Vascular complication
Procedural complication
Acute kidney injury
Unplanned revascularisation
Completeness of revascularisation
Health related quality of life/functional status
Resource utilisation and cost effectiveness
Serial cardiac troponin (T or I) levels
Length of stay

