7.4 Endpoint Definitions

Disabling Stroke	Stroke is defined as an acute episode of focal or global neurological dysfunction caused by brain, spinal cord, or retinal vascular injury as a result of hemorrhage or infarction, resulting in persistent moderate disability (modified Rankin Scale ≥ 3) at the time of discharge from the acute hospital admission.
Acute Myocardial Infarction	
1. Spontaneous MI (>48 hours after PCI/CABG) Detection of a rise and/or fall of cardiac Troponin I or T, with at least one value higher than the 99th percentile upper reference limit (URL) AND symptoms consistent with ischaemia OR dynamic electrocardiogram (ECG) changes (including ≥ 1mm ST elevation or ST depression, new left bundle branch block (LBBB) or >3mm T-wave inversion) OR imaging evidence of new loss of viable myocardium or new regional wall motion abnormality in a pattern consistent with an ischaemic aetiology.
 
2. Peri-procedural MI (<48 hours after PCI/CABG) Following PCI: Detection of a rise in cardiac troponin I or T, with the threshold of significance determined by the pre-procedure baseline value.
 
Baseline \leqURL: At least one value higher than five times the URL
 
Baseline $>$ URL and stable or falling: At least one value higher than 5xURL above the baseline value or 20% above the baseline value, whichever is greater.
 
Baseline $>$ URL and rising: At least one value higher than 5xURL above the predicted value* or 20% above the predicted value, whichever is greater.
 
*the predicted value will be calculated via linear extrapolation of the trend from at least two troponin values taken within 48 hours before the procedure.
 
Following CABG: As for PCI, but with a threshold of 10xURL. In addition to classifying patients dichotomously as having suffered a periprocedural MI or not, baseline and peak troponin I or T values measured within 24 hours of a procedure will be recorded. This will provide a continuous measure for adjudication of ties in patients reaching the periprocedural myocardial infarction endpoint within the Win Ratio.
 
Absolute values of troponin, ECGs and supporting information will be collected for all patients who experience a periprocedural MI, so that sensitivity analyses based on alternative definitions can be explored.

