- Step 5: Compare periprocedural MI. If only one has had a periprocedural MI, the patient who does not have a MI is the winner. If both have had a periprocedural MI, the patient with the smaller infarct size, as measured by peak Troponin level (expressed as a multiple of the 99th centile, to allow comparison of different Troponin assays) is the winner, unless the difference in increase in troponin level between patients is $\leq 5x$ the URL, in which case a tied will be declared. If neither patient has had a periprocedural MI, the stepwise comparison is concluded and the result declared a tie.

This approach is designed to optimise the impact of individual components of a composite endpoint, by allocating greater weight to more important events, increasing the range of events considered and allowing capture of recurrent events. The requirement for a $\geq 5x$ URL difference in troponin level in determining wins based upon peri-procedural MI is designed to ensure a clinically meaningful

difference in all declared wins. When analyses of recurrent events has been applied to simulated data and major contemporary heart failure trials precision has been shown to improve when treatment discontinuation is low following the first event[14]. Since the intervention is high-risk PCI and not drug therapy crossover rates are expected to be negligible allowing a smaller sample size whilst maintaining power. In contrast, a traditional composite endpoint trial using time to first event analysis weights each event equally and only incorporates the first event hence many more serious outcomes, such as death, may not included and no account is taken of later events. The sample size using such an approach would require a larger treatment difference to be detected (as illustrated below) or require a prohibitively large and expensive trial and would not be able to complete recruitment in a reasonable timeframe.

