10.2.2 Secondary Endpoints

Individual components of the hierarchical combined primary endpoint as well as repeated occurrences of these events, health-related quality of life, New York Heart Association (NYHA) functional class, completeness of revascularisation and resource utilisation at 90 days, yearly and at the end of the trial. The combined outcome and individual components will also be analysed using Cox proportional hazard models for the time-to-first event over the follow-up period. Other analyses such as sensitivity and per-protocol analyses will be detailed in the statistical analysis plan.

10.3 1-year feasibility review

A review of recruitment and pooled event rates was performed approximately one year after the first patient was recruited to inform the feasibility of completing the trial within the initial projected period. As the number of patients randomised was still relatively small and length of follow-up short, it was felt that the expected number of events at this stage of the trial was too low for meaningful assessment. Recruitment and the pooled event rate will continue to be monitored as the trial progresses.

An independent DMC has been established and a separate DMC charter developed which includes details of the meeting schedule and stopping guidelines. The DMC is expected to meet at least annually.

11. Screening

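### Does the 24-hour troponin, taken only in patients still in hospital, let detection of periprocedural MI differ between the arms?

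*Protocol*

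**What the plan says.** Section 19.4 gives the sampling schedule twice. The table marks troponin under both a 6-hour and a 24-hour post-procedure column, without conditions. The list below it keeps the 6-hour sample unconditional but puts the later one under "Post-procedure (24 hours after end of procedure if patient remains in hospital"). The discharge list has no troponin, and the table heads its discharge column "At discharge (up to 24 hours) post- PCI", so departure before the second sample appears to be foreseen.

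Section 7.4 defines periprocedural MI after PCI by at least one troponin value over a threshold within 48 hours. It adds that "baseline and peak troponin I or T values measured within 24 hours of a procedure will be recorded". It also says that "Absolute values of troponin, ECGs and supporting information will be collected for all patients who experience a periprocedural MI", so that alternative definitions can be explored.

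In Step 5 of section 10.1, a patient without a periprocedural MI beats a patient with one. If both have one, the winner is "the patient with the smaller infarct size, as measured by peak Troponin level", with a tie when the difference is no more than 5 times the upper reference limit (URL). MI also enters the endpoint in section 7.2, "Combined primary endpoint analysed with a time-to-first-event method", and the analysis of individual components. Section 7.3 lists "Serial cardiac troponin (T or I) levels" as a secondary endpoint. Section 10.2.2 states: "Other analyses such as sensitivity and per-protocol analyses will be detailed in the statistical analysis plan".

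**The concern.** Whether the second sample is taken depends on discharge, which happens after randomisation in an open-label trial. A patient sampled once has fewer chances to cross the threshold, and the recorded peak can only be equal or lower. If one arm goes home earlier, that arm could seem to have fewer and smaller infarcts with no true difference.

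Treatment could plausibly affect stay in either direction. Section 16.2 describes device weaning, vascular closure and possible transfer to critical care in the unloading arm. Section 2.2 hopes that unloading will shorten stay by preventing complications. At stake are Step 5, the time-to-first-event composite and the MI component.

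A second point arises beside it. For a raised and rising baseline, section 7.4 extrapolates from at least two troponin values within 48 hours before the procedure. Section 19.4 guarantees only one in that window.

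**Working it through.** The documents give no figure on this point: no discharge times by arm, no periprocedural MI rate and no ratio of 6-hour to 24-hour troponin. All inputs below except the sample size (300, so 150 per arm) and the Step 5 rules are assumptions. There is no true difference between arms throughout.

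**1. Detection rate.** Let p be the true MI rate, s the share of MIs detectable at 6 hours, and r the share of an arm with a 24-hour sample. The detected rate is p × [s + (1 − s) × r]. Take p = 20% and s = 0.7.
- r = 95%: 0.20 × (0.7 + 0.3 × 0.95) = 19.7%.
- r = 60%: 0.20 × (0.7 + 0.3 × 0.60) = 17.6%.
- The false difference is 2.1 points. It is zero if r is equal in both arms or if s = 1.

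**2. Step 5.** The 24-hour troponin is lognormal (sigma 1.3), scaled so that 30% of patients exceed 5 × URL. The 6-hour value is a fixed fraction of it. Leaving before 24 hours is 50% (control) and 10% (unloading), with patients of low troponin leaving first to a degree set by a correlation.

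| 6-hour / 24-hour | Correlation | Detected MI, control vs unloading | Step 5 win ratio |
|---|---|---|---|
| 0.5 | 0 | 22.2% vs 28.4% | 0.73 |
| 0.5 | 0.5 | 25.0% vs 29.5% | 0.82 |
| 0.5 | 0.8 | 27.6% vs 29.9% | 0.91 |
| 0.9 | 0.5 | not tabulated | 0.96 |

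With equal leaving (30% vs 30%), or with equal 6-hour and 24-hour values, it is 0.99 to 1.01. Values mirror above 1 if unloading patients leave earlier.

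**3. Whole win ratio.** If Steps 1 to 4 decide a share d of pairs symmetrically, and w and l are the Step 5 win and loss shares, the overall win ratio is [d/2 + (1 − d)w] / [d/2 + (1 − d)l]. A re-run of the first table row gives w = 0.175 and l = 0.239. With d = 50%, (0.25 + 0.0875) / (0.25 + 0.1195) = 0.91.
- Lowest value in any case tried (MI 10 to 40%): 0.902 at d = 50% and 0.953 at d = 73%.
- Mild case (MI 30%, fraction 0.7, correlation 0.5, leaving 30% vs 20%): about 0.99 at d = 50% and just under 1.00 at d = 73%.

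Simulated null trials of 150 per arm give a standard error of the log win ratio of 0.167 to 0.204 at d = 50% and 0.139 to 0.159 at d = 73%. The worst case is therefore ln(0.902) / 0.167 = −0.62 standard errors. The mild case is about ln(0.99) / 0.167 = −0.06.

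**4. Separate simulation.** Null trials with a different model (higher-tier events at 0.3 per year) gave mean win ratios of 0.95 to 0.98 under unequal coverage (95% vs 60% or 50%). Two-sided rejection was 4.6% to 6.2%. Rejection against unloading was 2.7% to 5.3%, against a nominal 2.5%.

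**5. Would a 6-hour-only analysis settle it?** In the model of step 2 it finds fewer MIs than the all-samples analysis: 5 to 14% fewer at a fraction of 0.9, 17 to 40% fewer at 0.7 and 34 to 65% fewer at 0.5. It also needs equal early kinetics. With fractions of 0.6 (unloading) and 0.7 (control) and MI 30%, its Step 5 win ratio is about 1.2 with no true difference. The all-samples analysis in the same setting, at correlation 0.5, gives 0.89 (leaving 50% vs 10%) or 0.96 (30% vs 10%).

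**The case for a change.** The strongest case for a change is that the existing safeguards do not reach this problem. Blinded adjudication cannot recover a sample that was never drawn. The alternative definitions promised in section 7.4 draw on patients with a detected MI, not on those missed. The serial troponin endpoint does not reclassify MI on equal sampling. Nor is Step 5 a negligible tier: section 10.2.1 supports the extension partly because longer follow-up may let higher tiers decide more pairs. At the extreme inputs, one-sided error against unloading roughly doubles. Reporting availability by arm costs almost nothing, and an analysis fixed before unblinding is more credible than one added later.

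The mechanism stands. The step from a possible difference to a defect in this protocol does not. It needs a gap between arms in discharge before 24 hours and troponin still rising after 6 hours, and neither appears in the documents. The larger shifts use assumed discharge gaps of 20 to 40 percentage points. Some of the difference in stay is also absorbed higher up: under section 7.4, qualifying prolongations of at least 24 hours count as cardiovascular hospitalisations and are compared at Step 4.

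The request for an availability table and a sensitivity analysis stands as sensible practice, but section 10.2.2 assigns such analyses to the statistical analysis plan. The protocol does not block them, since the 6-hour sample is scheduled for all and serial troponin is an endpoint.

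On the rising baseline, section 7.4 does not limit the two values to scheduled samples, and section 11.1 includes patients already admitted with acute coronary syndromes, who may well have more than the scheduled minimum. What remains is the lack of a stated fallback when only one recent value exists, which adjudication can settle.

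**Conclusion.** No change to the plan is needed. The difference between table and list in section 19.4 is a clerical slip: the list qualifies other plain table marks too, such as viability studies only where available. It can be tidied at any routine revision. Making the second sample depend on the patient still being in hospital is a fair trade-off between complete sampling and keeping patients in, or recalling them, for a blood test.

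The possible bias is conditional and its direction unknown. On assumed inputs it is well under a tenth of a standard error of the log win ratio in the mild case and about 0.6 in the most extreme. It would weigh more on the MI component and on Step 5 taken alone. It vanishes if early discharge is similar in the two arms or if 6-hour values are close to 24-hour values. Analysts can check the first directly by tabulating 24-hour samples by arm. A 6-hour-only analysis would be at most an optional companion, because a gap between it and the primary result could reflect early kinetics as easily as missed samples.
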